STATISTICAL ANALYSIS PLAN

Official Title:

Single-Layer Versus Double-Layer Uterine Closure After Primary Cesarean Section: Impact on Residual Myometrial Thickness and Cesarean Scar Defect Formation — A Prospective Randomized Controlled Trial

NCT Number: Pending

Protocol ID: 31/26

Document Date: April 23, 2026

Important Note: This Statistical Analysis Plan was finalized prior to database lock and unblinding. Any deviations from this pre-specified plan will be documented and justified in the final statistical report.

**Institution: Department of Obstetrics and Gynecology
Hedi Chaker University Hospital Sfax, Tunisia**

**Principal Investigator: [name], MD
Department of Obstetrics and Gynecology
Hedi Chaker University Hospital, Sfax, Tunisia
Email: [contact]**

**Supervisors: [name]
[name]
Department of Obstetrics and Gynecology**

Ethics Committee Approval: Ethics Committee of the Faculty of Medicine of Sfax, Tunisia

Approval Number: 31/26

STATISTICAL ANALYSIS PLAN (SAP)

Date of Finalization: April 2026

Responsible Statistician: [[name]]

Principal Investigator: [[name]]

SAP-1. GENERAL PRINCIPLES AND PURPOSE

This Statistical Analysis Plan (SAP) has been **prospectively written and finalized prior to database lock and unblinding**. Its purpose is to pre-specify all planned statistical analyses to minimize the risk of outcome reporting bias and post-hoc analytical decisions. Any deviations from this pre-specified plan will be documented with justification and transparently reported in the final statistical report.

All analyses will be conducted using:

- **SPSS version 26.0** (IBM Corporation) — primary analyses
- **R version 4.3** (R Foundation for Statistical Computing) — complementary and advanced analyses

SAP-2. ANALYSIS POPULATIONS

SAP-2.1 Intent-to-Treat (ITT) Population — PRIMARY

All randomized participants, analyzed according to the **treatment group to which they were allocated**, regardless of the actual treatment received or protocol deviations. This constitutes the **primary analysis population**.

SAP-2.2 Per-Protocol (PP) Population — SENSITIVITY

All randomized participants who:

- Received the allocated intervention as specified in the protocol
- Completed the **6-month follow-up visit** with a valid TVUS measurement
- Had no major protocol deviations affecting outcome assessment

SAP-2.3 Safety Population

All randomized participants who underwent the surgical intervention (regardless of which technique was ultimately performed).

Protocol deviations will be prospectively classified as **major** (potentially affecting primary outcome validity) or **minor** (unlikely to affect outcomes) and documented in a deviation log.

SAP-3. BASELINE CHARACTERISTICS

Baseline characteristics will be summarized for the **ITT population** by treatment group:

Variable Type	Summary Statistic
Continuous, normally distributed	Mean ± Standard Deviation
Continuous, non-normal distribution	Median (Interquartile Range, IQR)
Categorical	n (%)

Normality of continuous variables will be assessed using both the **Kolmogorov-Smirnov test** and the **Shapiro-Wilk test**, complemented by visual inspection of Q-Q plots and histograms.

Variables to be summarized include: age, BMI at delivery, gestational age, parity, indication for cesarean section, type of anesthesia, skin incision type, uterine exteriorization status, pre-operative hemoglobin and hematocrit, and attending surgeon (anonymized).

No inferential statistics (p-values) will be calculated for baseline comparisons, as any imbalances in a randomized trial result from chance rather than systematic bias (CONSORT Statement 2010).

SAP-4. PRIMARY OUTCOME ANALYSIS

Outcomes:

1. **RMT** at 6–8 weeks and 6–7 months (continuous, mm)
2. **CSD prevalence** at 6–8 weeks and 6–7 months (binary)

SAP-4.1 RMT — Unadjusted Analysis

- **If normally distributed:** Independent samples **t-test** (or Welch's t-test if unequal variances)
- **If non-normally distributed: Mann-Whitney U test**

Reported statistics:

- Mean \pm SD (or Median [IQR]) per group
- Mean difference (MD) with 95% Confidence Interval
- Two-sided p-value (significance threshold: $\alpha = 0.05$)
- Effect size: Cohen's d (t-test) or rank-biserial correlation (Mann-Whitney)

SAP-4.2 RMT — Adjusted Analysis (Primary)

A **multiple linear regression model** will be constructed:

Dependent variable: RMT at 6–7 months

Independent variables:

- Treatment group (primary predictor)
- Age (continuous)
- BMI (continuous)
- Gestational age (continuous)
- Uterine exteriorization (yes/no)
- Surgeon experience level (senior/resident Year 4–5)
- Duration of labor before cesarean section (if applicable)
- Indication for cesarean section

Model assumptions verified:

- Linearity (partial regression plots)
- Homoscedasticity (Breusch-Pagan test)
- Independence of residuals (Durbin-Watson test)

- Absence of multicollinearity (Variance Inflation Factor < 5)
- Normality of residuals (Shapiro-Wilk on residuals)

Reported: Adjusted MD (β coefficient) with 95% CI, R^2 , adjusted R^2 , F-statistic, overall model p-value

SAP-4.3 CSD Prevalence — Analysis

Unadjusted:

- Chi-square test or Fisher's exact test (if expected cell count < 5)
- Relative Risk (RR) with 95% CI
- Absolute Risk Reduction (ARR) and Number Needed to Treat/Harm (NNT/NNH)

Adjusted:

- **Binary logistic regression** at 6–8 weeks and at 6–7 months
- Covariates: same set as RMT regression model
- Variables with $p < 0.20$ in univariate analysis AND a priori confounders (age, parity, BMI, indication) included
- Model fit: **Hosmer-Lemeshow test**
- Multicollinearity: **Variance Inflation Factors (VIF)**
- Discrimination: **Area Under the ROC Curve (AUC)**
- Results expressed as adjusted **Odds Ratios (OR)** with 95% CI

SAP-5. SECONDARY OUTCOME ANALYSES

SAP-5.1 Continuous Secondary Outcomes

- Unadjusted: t-test or Mann-Whitney U as appropriate
- Adjusted: Multiple linear regression (same covariate set)
- Results: Mean difference or median difference with 95% CI

SAP-5.2 Binary Secondary Outcomes (Complications, Transfusion)

- Unadjusted: Chi-square or Fisher's exact test
- Results: RR, ARR, NNT/NNH with 95% CI

SAP-5.3 CSD Morphological Dimensions

Analyzed within the **CSD-positive subgroup only**:

- Depth, length, width: Mann-Whitney U test
- **CSD Volume** (ellipsoid formula): Mann-Whitney U test

SAP-5.4 Repeated Measures — RMT at 6 Weeks and 6 Months

Method: Linear Mixed-Effects Model (LME)

Model structure:

- Fixed effects: treatment group, time point (6 weeks vs. 6 months), treatment × time interaction
- Random effect: participant-level intercept (accounts for within-subject correlation)
- Covariance structure: Unstructured (preferred); compound symmetry if convergence issues

Interpretation:

- Significant interaction ($p < 0.05$): treatment effect differs across time points
- Non-significant interaction: main effects interpreted independently

SAP-5.5 Symptom Outcomes (Ordinal / Binary)

- Binary symptoms (spotting, dyspareunia): Chi-square or Fisher's exact test; RR with 95% CI
- **Paired temporal evolution** (6 weeks → 6 months within each group): **McNemar's test**
- Adjusted: Binary logistic regression

SAP-5.6 Hemoglobin Variation and Blood Loss

- ΔHb : t-test or Mann-Whitney U; mean difference with 95% CI
- PSTEV and PSTC: Mann-Whitney U (likely non-normal); median difference with 95% CI

SAP-6. ADVANCED ANALYTICAL METHODS

SAP-6.1 Clinical Predictive Model for CSD

A **clinical predictive model** for CSD formation will be developed using **Firth penalized logistic regression**, justified by the ratio of events to variables approaching the threshold defined by Peduzzi et al.

Model development:

- Variable selection: univariate screening ($p < 0.20$) + a priori clinical variables
- Stability: **Bootstrap validation (10,000 replications)**
- Optimal threshold: **Youden Index**
- Internal validation: **10-fold cross-validation** and **70/30 data partition**
- Performance: AUC, sensitivity, specificity, positive and negative predictive values

SAP-6.2 Mediation Analysis

The **mediating role of CSD at 6 weeks** on the relationship between hysterorrhaphy technique and RMT at 6 months will be assessed using the **counterfactual mediation framework (Imai et al.)**.

Estimated quantities:

- **ACME** (Average Causal Mediation Effect): indirect effect through CSD at 6 weeks
- **ADE** (Average Direct Effect): direct effect of technique on RMT
- **Total Effect** and **proportion mediated**

Method: Bootstrap with **10,000 replications**

Sensitivity analysis: Critical ρ (rho) analysis to quantify robustness to unmeasured confounders

SAP-6.3 Inter-Operator Homogeneity

Breslow-Day test for homogeneity of treatment effects across operators (surgeons), to assess whether results are consistent regardless of the individual performing the procedure.

SAP-6.4 Measurement Reproducibility

Inter-observer concordance will be evaluated by **double-blind reading (n = 30 randomly selected examinations)**:

- Continuous variables (RMT, AMT): **Intraclass Correlation Coefficient (ICC)**
- Categorical variables (CSD presence): **Cohen's Kappa**

Temporal concordance of RMT measurements (6 weeks vs. 6 months):

- **Lin's Concordance Correlation Coefficient**
- **Bland-Altman analysis** (mean difference and limits of agreement)

SAP-7. SUBGROUP ANALYSES

Pre-specified subgroup analyses for the primary outcome (RMT at 6–7 months):

Subgroup Factor	Categories	Statistical Test
BMI category	< 30 vs. 30–34.9 kg/m ²	Interaction term in regression
Gestational age	37–38+6 vs. ≥ 39 weeks	Interaction term
Indication for CS	Labor dystocia vs. Fetal indication vs. Maternal indication	Interaction term
Uterine exteriorization	Yes vs. No	Interaction term
Type of cesarean section	Scheduled vs. Intrapartum	Interaction term
Surgeon category	Senior vs. Resident Year 4–5	Interaction term

Test for interaction: Likelihood ratio test comparing models with and without the interaction term.

All subgroup analyses are exploratory and hypothesis-generating. No correction for multiple comparisons is applied to subgroup analyses; results will not drive primary conclusions.

Results will be presented in **forest plots**.

SAP-8. SENSITIVITY ANALYSES

Analysis	Method
SA-1: Per-Protocol population	Repeat primary analysis in PP population
SA-2: Intraoperative complication exclusion	Exclude participants with major intraoperative events (corporeal hysterotomy, hysterotomy extension > 2 cm)
SA-3: Multiple imputation for missing RMT	MICE — 5 scenarios: observed data, LOCF, best case, worst case, 6-week status carry-forward
SA-4: Inverse Probability Weighting (IPW)	Adjust for informative loss to follow-up
SA-5: Binary threshold analysis	Proportion with RMT < 2.5 mm and RMT < 3.0 mm; Chi-square test
SA-6: Complete case analysis	For comparison with imputed results

SAP-9. MULTIPLICITY AND TYPE I ERROR CONTROL

- **Primary outcomes:** $\alpha = 0.05$, two-sided, for each co-primary endpoint (RMT and CSD prevalence at 6 weeks and 6 months)
- **Secondary outcomes:** Exploratory; **Holm-Bonferroni correction** applied to control family-wise error rate
- **Unmeasured confounders:** **E-value** calculated to quantify the minimum strength of an unmeasured confounder needed to explain away observed associations

SAP-10. MISSING DATA STRATEGY

Data Type	Strategy
Primary outcome (RMT at 6 months)	Five imputation scenarios (MICE)
Secondary continuous outcomes	Complete case + sensitivity with imputation if > 10% missing
Binary outcomes	Complete case analysis

Symptom questionnaires	Linear mixed model (full information maximum likelihood)
------------------------	--

Missing data mechanism assessed by **Little's MCAR test**.

Participants lost to follow-up compared to completers on key baseline variables; reasons for dropout documented and reported.

SAP-11. PRESENTATION OF RESULTS

Results reported in accordance with **CONSORT 2010** guidelines:

- **Table 1:** Baseline characteristics (ITT population) — no p-values
- **Figure 1:** CONSORT flow diagram
- **Table 2:** Primary and secondary outcomes with between-group comparisons
- **Table 3:** Subgroup analysis (forest plots)
- **Table 4:** Multivariate analysis results
- **Table 5:** Safety and adverse event summary
- **Figure 2:** Bland-Altman plot for RMT reproducibility
- **Figure 3:** ROC curve for predictive model

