7.2 Allocation Timing and Procedure

The group allocation is revealed to the operating surgeon **on the day of the intervention only**, under the following sequential conditions:

1. **Verification of all eligibility criteria**

2. **Signed informed consent obtained**
3. **Fetal delivery and placental delivery completed**
4. **Immediately before performance of hysterorrhaphy**

This sequential allocation procedure ensures that randomization occurs as late as operationally feasible, maximizing allocation concealment and minimizing contamination.

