8. INTERVENTIONS

8.1 Common Standardized Surgical Elements (Both Groups)

All cesarean sections are performed by **senior gynecologist-obstetricians or fourth- and fifth-year obstetric residents**, all experienced in both hysterorrhaphy techniques, according to a **strictly standardized operative protocol** from anesthesia to parietal closure. The only variable between groups is the hysterorrhaphy technique; all other operative steps are conducted uniformly.

Standard protocol elements include:

- **Anesthesia:** Spinal or general (recorded)
- **Skin incision:** Pfannenstiel or Joel-Cohen technique (recorded)
- **Fascial incision:** Transverse
- **Peritoneal entry:** Sharp or blunt (recorded)
- **Uterotomy:** Low transverse hysterotomy

- **Uterine exteriorization:** At surgeon's discretion (recorded)
- **Placental delivery:** Standardized technique
- **Peritoneal closure:** Not performed in either group
- **Fascial closure:** Continuous absorbable suture
- **Skin closure:** Subcuticular absorbable suture
- **Prophylactic antibiotics:** Standard institutional protocol

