6. PRIMARY OUTCOME STATISTICAL ANALYSIS

6.1 RMT Analysis

Step 1 — Unadjusted:

If normally distributed	Independent t-test (or Welch's t-test)
If non-normal	Mann-Whitney U test

Step 2 — Adjusted (primary analytical approach):

Multiple linear regression with RMT as dependent variable

Covariates: Treatment group, age, BMI, gestational age, uterine exteriorization, surgeon category, labor duration, CS indication

Reported: Adjusted MD, 95% CI, R^2 , adjusted R^2 , F-statistic, model p-value

Assumption verification: Linearity, homoscedasticity (Breusch-Pagan), independence (Durbin-Watson), multicollinearity ($VIF < 5$), normality of residuals (Shapiro-Wilk)

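### The primary RMT regression gives scheduled caesareans no labour-duration value, so they could be deleted, and it adjusts for exteriorization, which is not fixed before allocation is revealed

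*SAP*

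**What the plan says.** The heading "SAP-4.2 RMT — Adjusted Analysis (Primary") makes the multiple linear regression of RMT at 6–7 months the main analysis. Its covariates include "Duration of labor before cesarean section (if applicable") and "Uterine exteriorization (yes/no"). Section 6.1 of the SAP in the combined document also treats the adjusted model as the primary approach. It lists "uterine exteriorization, surgeon category, labor duration, CS indication", without the qualifier about applicability.

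Protocol section 6.1 recruits scheduled caesareans and section 6.2 recruits caesareans in labour. SAP-7 plans an interaction test for "Scheduled vs. Intrapartum". Both SAPs take every randomized woman as the primary population. The missing-data sections (SAP-10, and section 12 of the combined document's SAP) give rules for outcomes and none for covariates.

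Protocol section 8.1 describes exteriorization as "At surgeon's discretion (recorded"). Section 7.2 reveals the allocation to the surgeon after "Fetal delivery and placental delivery completed" and "Immediately before performance of hysterorrhaphy". Section 7.3 lists the surgeon as unblinded. SAP-3 summarizes exteriorization among the baseline characteristics, and SAP-7 uses it as a subgroup factor.

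**The concern.** The two covariates raise separate problems in the same model.

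**Labour duration.** A woman with a scheduled caesarean has no labour to time. Unless told otherwise, linear regression in SPSS or R omits any record with a blank covariate. A blank field would therefore turn the primary model into an intrapartum-only analysis. The scheduled-versus-intrapartum interaction could then not be estimated if it is fitted on the same covariate set. Leaving the field blank, coding it 0 and omitting the term are all consistent with the text, and they give different primary models. The standalone SAP is dated April 2026, after recruitment was due to end in December 2025, so the choice would be made once data exist.

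**Exteriorization.** A covariate in a primary randomized comparison should be fixed before allocation can influence it. Nothing in the protocol guarantees that here. If surgeons exteriorize more often in one arm because of the closure they are about to perform, exteriorization lies on the path from technique to RMT. Adjusting for it then no longer estimates the total effect of technique.

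The covariate set is reused for the CSD logistic model (SAP-4.3) and the continuous secondary outcomes (SAP-5.1), so both problems carry over.

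**Working it through.** **The plan's own figures.** Protocol section 11 gives α = 0.05 two-sided, 80% power, SD 3.5 mm, difference 1.3 mm, 30% loss and 192 enrolled per group.
- n = 2 × (1.96 + 0.842)² × 3.5² / 1.3² = 113.8, so 114 per group. This reproduces.
- 114 / (1 − 0.30) = 162.9, so 163 per group. This reproduces.
- Evaluable from the 192 enrolled: 192 × 0.70 = 134.4 per group.

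**Power if scheduled women are deleted.** Let s be the scheduled share. The documents do not give it, so 10–50% is an assumed range, taken as equal in both arms and with the same loss to follow-up. Retained per group: n = 134.4 × (1 − s). Power is for the two-sided two-sample t-test with non-centrality 1.3 / (3.5 × √(2/n)) and 2n − 2 degrees of freedom, ignoring any gain from covariates.

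| s | n per group | Power |
|---|---|---|
| 0 (no deletion) | 134.4 | 85.9% |
| 10% | 121.0 | 82.0% |
| 20% | 107.5 | 77.4% |
| 30% | 94.1 | 71.7% |
| 40% | 80.6 | 65.0% |
| 50% | 67.2 | 57.0% |

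The normal approximation gives values 0.2 to 0.6 percentage points higher. The retained number reaches the planned 114 at s = 1 − 114/134.4 = 15.2%.

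**Exteriorization.** With treatment and exteriorization as the only regressors, least squares gives: unadjusted minus adjusted treatment coefficient = (arm difference in exteriorization rate) × (fitted coefficient of exteriorization). Neither factor is in the documents. Assumed ranges:
- Arm difference 0.10, coefficient 0.5 mm: shift 0.05 mm, and 0.05/1.3 = 4% of the target difference.
- Arm difference 0.30, coefficient 1.0 mm: shift 0.30 mm, and 0.30/1.3 = 23%.

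If the rate is the same in both arms, the shift is zero in expectation. A simulation with 134 per group, 2,000 runs and a true effect of 1.3 mm gave 1.29 mm with and without adjustment. A second simulation had a 20-point arm difference, a −0.5 mm effect of exteriorization and an unmeasured common cause. It gave 1.21 mm unadjusted and 1.19 mm adjusted, because the direct effect and the confounding nearly cancelled. Arm-dependence therefore makes bias possible, but its size is unknown.

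**The case against.** A reader might infer that the plan drops scheduled caesareans. The documents do not say so. The applicability qualifier shows that the authors knew some women have no labour. The intention-to-treat definition and the planned scheduled-versus-intrapartum subgroup both imply that these women are meant to be analysed, and coding them 0 would keep them. SAP-7 also does not say that its interaction models carry the full SAP-4.2 covariate set. This stands: deletion is a consequence of running the model with blanks, not a stated intention. At a 10% scheduled share, power would still exceed 80%.

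A reader might also infer that surgeons choose exteriorization after seeing the allocation. The documents do not show this either. Protocol section 8.1 states that closure technique is the sole difference between arms and that the remaining steps are uniform. Section 7.2 puts the reveal very late, which leaves a narrow window. Section 8.1 lists exteriorization before placental delivery, although that list is not stated to be chronological. This limits the likelihood of bias. It does not settle the matter, because the same section leaves exteriorization to the surgeon and no timing is specified.

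The unadjusted comparison in SAP-4.1 and the mixed model in SAP-5.4 contain neither covariate, so a distortion could be seen beside them. Neither is the analysis labelled primary, so this mitigates the problem without removing it.

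**Conclusion.** The concern holds as a gap in the primary model with two parts. The first is the more important because it decides who is analysed. Labour duration has no defined value for scheduled caesareans and no covariate rule covers them, so an ordinary regression would delete them unless coding is specified. The power loss is conditional on that deletion and on a scheduled share the documents do not give. It runs from about 4 percentage points at 10% to about 29 at 50%, and the evaluable number drops below plan above about 15%. It is not established that the primary estimate will be intrapartum-only.

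The second part is that exteriorization is not guaranteed to be a pre-allocation variable. Bias arises only if its use depends on arm, which is possible but not shown. Under the assumed inputs the coefficient would move by 0.05 to 0.30 mm. It is also not supported to call it a baseline characteristic, as SAP-3 does.

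**What to change.** - First confirm that labour duration was recorded. It is not named in the SAP-3 list or in the collection schedule in protocol section 10.
- Replace the labour covariate with two terms: labour before caesarean (yes/no), and hours of labour set to 0 when there was none.
- State that every intention-to-treat woman with an RMT measurement enters the model. Apply the same coding to the CSD and secondary models that reuse the set. In the scheduled-versus-intrapartum subgroup model, watch for overlap between that factor and the labour indicator.
- Take exteriorization out of the primary covariate set unconditionally. Making this depend on later inspection of records would leave the primary model open.
- Report exteriorization by arm as an intraoperative descriptive, not a baseline variable. Keep the exteriorization-adjusted model as a sensitivity analysis, and keep its subgroup result as exploratory with a caveat that the factor may follow allocation.

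The cost is SAP wording and recoding, with no new data if labour duration was collected. The downside is a possible small loss of explained variance if exteriorization is prognostic. The documents give no figure for this.

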3.2 Secondary Objectives

1. To compare **intraoperative parameters** between groups, including hysterorrhaphy duration, total operative time, visually estimated blood loss (PSTEV), calculated total blood loss (PSTC), number of additional hemostatic sutures, and intraoperative complications.
2. To assess **immediate postoperative outcomes**, including hemoglobin variation (ΔHb), transfusion requirement, early postoperative complications (endometritis, wound infection, parietal hematoma, thromboembolic events, surgical revision), and hospital length of stay.
3. To evaluate **medium-term gynecological symptoms** potentially attributable to CSD at 6 weeks and 6 months, including postmenstrual spotting, prolonged menstruation (> 7 days), dysmenorrhea, chronic pelvic pain, menometrorrhagia, and dyspareunia.
4. To compare **CSD morphological characteristics** between groups, including defect depth, length, width, and estimated volume using the ellipsoid formula.
5. To assess the **adjacent myometrial thickness (AMT)** and the **myometrial ratio ($\text{RM} = \text{RMT}/\text{AMT} \times 100$)** at both evaluation time points.
6. To identify **clinical and surgical predictors** of CSD formation and reduced RMT.
7. To evaluate the **mediating role** of CSD at 6 weeks on RMT at 6 months.

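### The Durbin-Watson test cannot show that residuals in the adjusted RMT model are independent of surgeon; if surgeons differ, the senior/resident and overall-model p-values are too small, while the treatment p-value holds

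*SAP*

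**What the plan says.** SAP-4.2 makes a multiple linear regression of RMT at 6–7 months the primary adjusted analysis. Among the assumptions to be verified is "Independence of residuals (Durbin-Watson test". The SAP inside the combined document repeats it in section 6.1: "independence (Durbin-Watson". Neither place gives a row order, a cut-off, or what happens if the check fails.

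The closures are done by "senior gynecologist-obstetricians or fourth- and fifth-year obstetric residents" (protocol section 8.1). The regression represents the operator only by "Surgeon experience level (senior/resident Year 4–5". Individual identity is recorded, since SAP-3 lists "attending surgeon (anonymized" among the variables to summarise, but it does not enter the regression. There is no surgeon effect, fixed or random, and no cluster-robust standard error.

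The reported results include "F-statistic, overall model p-value". Secondary objective 6 in protocol section 3.2 reads "To identify clinical and surgical predictors of CSD formation and reduced RMT".

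**The concern.** The Durbin-Watson statistic measures lag-1 correlation in the order of the rows. In a file with one row per woman, that order is a filing choice, so re-sorting can change the answer. The dependence that is plausible in this design is between women closed by the same surgeon, and those women need not sit next to each other.

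A reassuring result could therefore be reported as verified independence when it verifies nothing of the kind. What is at stake is inference on terms that vary between surgeons. The senior/resident coefficient compares groups of surgeons, yet ordinary least squares (OLS) treats every woman as an independent piece of evidence on it. The overall model F-test includes that term and inherits part of the error.

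**Working it through.** **The plan's own figure.** n = 2 × (1.96 + 0.842)² × 3.5² / 1.3² = 113.8, so 114 per group, as stated in protocol section 11. The documents give no figure for surgeon clustering.

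**Inputs.** Enrolment is 192 per group with 30% loss anticipated: 192 × 0.70 = 134.4, so about 134 per group and 268 women. Assumed, because the documents are silent: K = 10 to 30 surgeons and ICC = 0.05 to 0.10, with a wider range where stated.

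**What Durbin-Watson can see.** d = Σ(eᵢ − eᵢ₋₁)² / Σeᵢ² ≈ 2(1 − r₁), where r₁ is the correlation between neighbouring rows. If row order is unrelated to surgeon, the expected r₁ is about −1/(n − 1) = −1/267 = −0.004 whatever the ICC, so there is nothing to detect. If the next row has the same surgeon with extra probability p, then r₁ ≈ p × ICC, against a standard error of 1/√268 = 0.061. For p = 0.40 and ICC = 0.10, r₁ ≈ 0.04 and z = 0.04/0.061 = 0.65. One-sided power is then P(Z > 1.645 − 0.65), about 16%; simulation gives 16.4%.

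**What OLS does to the senior/resident term.** With m = 268/K women per surgeon, the variance of a between-surgeon contrast is understated by about 1 + (m − 1) × ICC. The type I error is then 2 × [1 − Φ(1.96/√(1 + (m − 1) × ICC))]. For K = 10 and ICC = 0.10: m = 26.8, the factor is 1 + 25.8 × 0.10 = 3.58, 1.96/√3.58 = 1.036, and the error is 0.30.

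**Simulation** (268 women, 1,500 trials per cell, rows in random order, no true senior/resident effect):

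| K | ICC | Durbin-Watson rejects | Direct F-test of surgeon rejects | Senior/resident type I error, simulated | By formula |
|---|---|---|---|---|---|
| 10 | 0.05 | 4.5% | 60% | 19% | 19.5% |
| 10 | 0.10 | 5.0% | 86% | 30% | 30.0% |
| 20 | 0.05 | 4.0% | 48% | 12% | 12.4% |
| 20 | 0.10 | 5.3% | 83% | 20% | 19.0% |
| 30 | 0.05 | 4.4% | 38% | 10% | 9.7% |
| 30 | 0.10 | 5.5% | 78% | 15% | 14.3% |

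At ICC = 0 all three simulated rates are about 4–6%.

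**Dependence on file order.** Enrolment averages 384/365 = 1.05 women a day. Under a Poisson assumption the next woman falls on the same day with probability 1 − (1 − e^(−1.05))/1.05, about 0.38, so some same-surgeon runs are plausible. With 15 surgeons and ICC 0.05–0.20, one-sided detection is 8–16% at a repeat probability of 0.25 and 9–31% at 0.40. With rows sorted by surgeon it is 14–80%, the top of that range needing strong clustering.

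**Other terms and the remedy.** These runs used 8, 15 and 30 surgeons.
- Overall F-test, type I error: 13%, 9% and 7% at ICC 0.05; 21%, 14% and 8% at ICC 0.10.
- Treatment coefficient: about 4–6% throughout, which is nominal.
- With a surgeon random intercept and K − 2 degrees of freedom, the senior/resident term returns to 4.5–5.6% (ICC 0.05–0.20).
- Removing surgeon variance multiplies the treatment standard error by √0.95 = 0.975 to √0.90 = 0.949, a cut of about 3–5% at most. Power for 1.3 mm with 15 surgeons and ICC 0.10 moves from 85.5% to 87.3%.

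**The case against.** **The treatment test is unaffected.** This stands. A reader might infer that the primary comparison is invalid or the sample size too small for clustering. The documents do not support that, because allocation is individual and 1:1, so both techniques can occur within each surgeon's patients. Treatment type I error would rise only if the treatment effect itself varied by surgeon (8–15% with 15 surgeons and 11–23% with 8, for slope variance of 5–20% of the total). Nothing in the documents shows such variation, and a random intercept alone has not been shown to cure it.

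**The ICC may be zero.** This stands as a condition. Section 8.1 prescribes a standardized operation by surgeons experienced in both techniques. That makes a small ICC possible but does not establish it, and at zero no p-value is wrong.

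**No conclusion is tied to the senior/resident coefficient.** This stands in part. The only predictor model specified, SAP-6.1, concerns CSD, and the plan does not say that SAP-4.2 serves objective 6. But that objective also names reduced RMT, SAP-11 gives the multivariate results a table, and the overall p-value is reported in any case.

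**Surgeons are examined elsewhere.** SAP-6.3 plans a "Breslow-Day test for homogeneity of treatment effects across operators (surgeons", and SAP-7 tests a surgeon-category interaction. The first concerns odds ratios for a binary outcome and the second a difference in treatment effect by grade. Neither addresses correlated RMT residuals. The mixed model in SAP-5.4 has a participant intercept only.

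**Durbin-Watson has a use.** If rows follow enrolment over the 12-month recruitment, it can reveal drift. This stands, so the test need not be deleted.

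**Conclusion.** The concern holds in a limited form. Whatever the ICC, Durbin-Watson is the wrong instrument for the independence assumption it is meant to verify. About 5% rejection is its floor, reached when row order is unrelated to surgeon. It is not a general detection rate: same-surgeon runs raise it to roughly 8–30%.

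The consequence for p-values is conditional on a non-zero surgeon ICC. With 10–30 surgeons and ICC 0.05–0.10, both assumed, the senior/resident test has a type I error of about 10–30%, and the overall F-test is inflated by less. This is worth correcting because surgeon-level results will be available to interpret and the data needed are already collected. It gives no reason to doubt the primary treatment p-value.

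**What to change.** In SAP-4.2 and section 6.1 of the combined document:

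1. Stop citing Durbin-Watson as evidence of independence. If it is kept, describe it as a check for drift with rows in enrolment order.
2. Fit the adjusted RMT model with the same covariates plus a random intercept for the anonymized surgeon ID, either as the adjusted model or as a pre-specified companion to it.
3. Report the surgeon ICC and the number of surgeons.
4. Take any senior-versus-resident p-value and interval from that model, with surgeon-level degrees of freedom (K − 2) or a small-sample method such as Kenward-Roger.

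No new data are needed, and R with lme4 is already planned. The price is one further mixed model, for which the OLS R² and F-statistic do not carry over directly. Making it the adjusted model would also mean restating the sensitivity and interaction analyses built on the regression; the companion option avoids that. Kenward-Roger may need a package beyond those listed, whereas K − 2 does not. The change should be dated before database lock, or else reported as a deviation.
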